6.2.2 FORMULATION, APPEARANCE, PACKAGING, AND LABELING

CD24Fc is supplied as a sterile, clear, colorless, preservative-free aqueous solution for parenteral administration, in a clear borosilicate glass vials with chlorobutyl rubberstoppers and aluminum flip off seals. CD24Fc is formulated as single dose injection solution, at a concentration of 10 mg/mL at pH of 7.2. Each CD24Fc vial contains 120 mg of the fusion protein in 12 ± 0.2 mL injection solution. CD24Fc is stored at -20° C until use. CD24Fc should be thawed to room temperature prior to administration. New CD24Fc Drug Product has been manufactured as "Lot 0118-002". Stability studies for Lot 0118-002 are ongoing and it has demonstrated to be stable for 12 months at the intended storage temperature, - 20°C, for 6 months at 5°C and 1 month at 25°C. The area in which the investigational product is stored must be locked, with limited access only to unblinded study personnel and the temperature must be monitored.

Each study vial will be labeled according to Title 21 of the U.S. Code of Federal Regulations. Each vial product label will contain the following information:

- Product name (CD24Fc)
- Lot number
- "Caution: New Drug- Limited by Federal (or United States) law to investigational use"
- 120mg/vial, 10mg/mL in 12.0 mL
- Storage Condition: -20 degrees Celsius
- "DO NOT SHAKE OR DROP THE VIAL"
- Oncolmmune, Inc.

6.2.3 PRODUCT STORAGE AND STABILITY

CD24Fc must be stored between -15°C and -25°C. If a temperature excursion should occur, the investigational product will be quarantined and the Temperature Excursion Report Form will be completed and sent to the Sponsor at for approval prior to proceeding with use of the investigational product.

CD24Fc is stored at -20° C until use. CD24Fc should be thawed and equilibrated to room temperature prior to administration. Stability studies for Lot 0118-002 are ongoing and it has demonstrated to be stable for 12 months at the intended storage temperature, -20°C, for 6 months at 5°C and 1 month at 25°C.

6.2.4 PREPARATION

The constituted drug infusion solution should be prepared by a trained medical professional using aseptic technique by the following procedure:

- 1. Determine the volume of CD24Fc solution: 240 mg per infusion with a volume of 24 ml from 2 vials.
- Parenteral drug products should be inspected visually before and after reconstitution for particulate matter and discoloration prior to administration, whenever solution and container permit. If visibly opaque particles, discoloration or other foreign particulates are observed, the solution should not be used.
- 3. Calculate the volume of sterile 0.9% Sodium Chloride Injection, USP, required: 76 ml in volume to reach a final volume of 100 ml.
- 4. Using an empty IV bag, add the above 76 ml volume of sterile 0.9% Sodium Chloride followed by the 24 ml volume of CD24Fc solution. Gently mix.
- 5. The CD24Fc infusion should begin within 6 hours of reconstitution and dilution. The infusion must be administered over a period of not less than 60 minutes for dose of 240 mg. An infusion set with an in-line, sterile, non-pyrogenic, low-protein-binding filter (pore size of 1.2 μm or less) must be used.
- 6. At the end of infusion, add a small amount of normal saline (25 ml) to the infusion bag to ensure the entire volume of study drug is infused.

For the placebo, the preparation will be as follows.

- 1. Calculate the volume of sterile 0.9% Sodium Chloride Injection, USP, required: 100 ml in volume to reach a final volume of 100 ml.
- 2. Using an empty IV bag, add the above 100 ml volume of sterile 0.9% Sodium Chloride.
- 3. The CD24Fc or placebo infusion should begin within 3 hours of reconstitution and dilution. The infusion must be administered over a period of not less than 60 minutes for dose of 240 mg. An infusion set with an in-line, sterile, non-pyrogenic, low-protein-binding filter (pore size of 1.2 μm or less) must be used.

4. At the end of infusion, add a small amount of normal saline (25 ml) to the infusion bag to ensure the entire volume of study drug is infused.

6.3 MEASURES TO MINIMIZE BIAS: RANDOMIZATION AND BLINDING

This is a randomized, double-blinded, placebo-controlled trial. Subjects will be randomized using block randomization in a 1:1 ratio of CD24Fc:placebo. They will be block randomized in blocks of six (except for the last block of four). The first block of six will all have PK analyses and there will be a safety and efficacy review upon completion of dosing by this group of six without halting enrollment.

Every effort will be made to minimize the various known sources of bias. Breaking the blind will be considered only when knowledge of the treatment assignment is deemed essential by the subject's physician for the subject's care. Any intentional or unintentional breaking of the blind will be reported to the sponsor and IRB, and explained at the end of the trial, irrespective of the reason for its occurrence.

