1.3 SCHEDULE OF ACTIVITIES (SOA)

	Screening ⁺ Day -55 to - 14	Day -55 to -1	Day -55 to -1#	Day 0	Wk 2*	Wk 4*	Wk 6^	Wk 16^	Wk 28^
Informed Consent	Х								
Medical History & Physical Exam ¹	Х			Х			Х	Х	Х
Height, Weight, and BMI	Х								Х
Vital Signs	Х			Х	Х	Х	Х	Х	Х
Medication Reconciliation	Х			Х	Х	Х	Х	Х	Х
Adverse Event Review and Evaluation				Х	Х	х	Х	Х	х
CMP, CBC with diff, PT/INR, Urinalysis	Х			Х	Х	Х	Х	Х	Х
CD4 count and HIV VL	Х			Х	Х	Х	Х	Х	Х
Hepatitis B panel (surface antigen, core antibody, surface antibody)	Х								
Hepatitis C Ab with reflex RNA	Х								
Hemoglobin A1c	Х						Х		Х
Lipid panel (Fasting)	Х		Х	Х	Х	Х	Х	Х	Х
Troponin I and T	Х						Х		Х
Leptin (Fasting)	Х		Х				Х		Х
ECG (once at Screening and Wk 6; pre-dose and 2 hrs post-dose during dosing visits)	х			Х	Х	Х	Х		
Serum hCG (women of child-bearing potential)	Х								Х
POC Urine hCG (women of child-bearing potential)				Х	Х	Х	Х	Х	
PK of ART and CD24Fc before (and 2 hrs post-dose for Day 0 to Week 4)- first 6 subjects				Х	Х	Х	х	Х	х
Anti-drug antibody%				Х			Х		Х
Immunology labs (for CD4:CD8, sCD14, proviral DNA), inflammatory cytokines	Х			х	Х	х	х	х	х
GlycA, CEC, NMR lipoproteins ²				Х			Х		Х
hsCRP, IL-6, apoB, Lp(a), UACR	Х			Х	Х	х	х	х	Х
Endothelin-1	Х								Х
CD24Fc Infusion		Ī		Х	Х	Х			
Transient elastography with CAP	Х		х						Х
FDG PET/CT (NIH) ³		Х							Х

* Screening tests within the last 8 weeks prior to screening visit that have been done as part of routine medical care or at an outside

facility can be used. Screening window of 8 weeks with more than 2 weeks between screening and Day 0.

*Study Visits for Weeks 2-4 include a window of +/-4 days

^Study Visit for Weeks 6, 16 and 28 include a window of +/- 1 week except for FDG PET/CT, which will include a window of +/-30 days

¹ Targeted history and exam will be performed as needed for symptoms or lab abnormalities

 $^{\rm 2}$ Only for subjects completing the optional FDG-PET/CT testing

³ See protocol section 8.1.1.2 for criteria leading to FDG PET/CT testing

If subject is not fasting at screening, may return for fasting labs and Transient Elastography prior to Day 0

% also done for suspected immune-related adverse events.

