3.1.3 EXPLORATORY OBJECTIVES

- 1. To assess the effect of CD24Fc on aortic vascular inflammation as measured by standardized uptake value of arterial FDG by PET/CT. We will select 12 subjects with an LDL>125 to have the imaging study.
- 2. To assess the effect of CD24Fc on the inflammatory markers hs-CRP and GlycA.
- 3. To assess the effect of CD24Fc on the CEC and NMR lipoproteins.
- 4. To assess the effect of CD24Fc on endothelin-1.

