8.1.1.2 FDG-PET/CT VISIT

Twelve subjects will undergo FD -PET/CT to assess aortic inflammation at NIH. These participants will have an LDL>125. Subjects will have an FDG-PET/CT after screening, but prior to Day 0 and at week 28. Subjects will be provided transportation to and from the NIH if needed.

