Although CD24Fc is not expected to have anti-viral activity, preliminary studies in humanized mice and non-human primate models ³⁰, showed that CD24Fc significantly reduced viral burden in vivo, including proviral burden in the PBL of SIV-infected Macaques rhesus, perhaps by preventing T cell over-activation and its associated exhaustion immunity³⁰. This hypothesis will be tested in ART-treated HIV infected subjects by longitudinal analysis of proviral titers. Established methods for quantification of proviral DNA (droplet digital PCR) will be used as described^{31,32}. Droplet digital PCR will be conducted to quantitate the frequency of cells carrying HIV proviral DNA and cell-associated HIV RNA with single copy sensitivity. The level of replication-competent/infectious HIV in the CD4⁺ T cell compartment will be determined by quantitative coculture assays.

• Inflammatory cytokines

Peripheral blood mononuclear cells will be isolated using Ficoll-Hypaque density gradient technique and used for immunophenotyping. Cells will be washed and stained using appropriate panels of monoclonal antibodies that distinguish cell type (B, T NK, monocyte etc.), cellular

activation states (CD14, CD38, HLA DR, CD25, etc.) and their ability to secrete inflammatory cytokines (IFN, TNF) using intracellular cytokine staining using a 12 color flowcytometry analysis with FlowJo software, at the University of Maryland.

- CD4 and CD8 T cell counts and ratio
 T cell immunophenotyping will be performed as a clinical laboratory test using flow cytometry at the University of Maryland.
- GlycA, plasma. This is a heterogeneous nuclear magnetic resonance signal originating from mobile glycan residues on plasma glycoproteins, used as a novel composite biomarker of systemic inflammation. This assay will be done at the NIH for those subjects completing the optional FDG-PET/CT.
- CEC- cholesterol efflux capacity, plasma. This is an assay assessing HDL function using the macrophage J774 efflux system. This assay will be done at the NIH for those subjects completing the optional FDG-PET/CT.
- NMR lipoproteins, plasma. This is an assay looking at lipoprotein particle size and number using NMR spectroscopy. This assay will be done at the NIH for those subjects completing the optional FDG-PET/CT.
- Endothelin-1, plasma. An ELISA test will be done for subjects at screening and week 28 to look for changes in endothelin-1, which may indicate changes in pulmonary arterial pressure.

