2 NIH PATIENT REGISTRATION

2.1 REGISTRATION PROCEDURES

2.1.1 REGISTRATION PROCESS AT NIH

Screening and enrollment into this study was performed at the University of Maryland in accordance with the sponsor protocol section **7.1 Study Visits and 7.1.1.1 Screening**. After the subjects meets the eligibility and signs the consent document, 12 subjects will be selected to travel to the NIH CC for the optional FDG PET/CT scans. Authorized member of the research team will make a request in the Admission Travel Voucher (ATV) system and have a medical record number assigned. Subject will then be registered in NIH Clinical Research Information System (CRIS). Both ATV and CRIS systems are password protected with access granted only to authorized personnel.

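### Randomisation is not stratified by imaging participation, so the arm split of the 12 FDG-PET/CT participants, the only source of TBR, GlycA, CEC and NMR lipoproteins, is left largely to chance

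*Combined protocol and SAP*

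**What the plan says.** Section 6.3 sets the allocation: "Subjects will be randomized using block randomization in a 1:1 ratio of CD24Fc:placebo". On the blocks it adds: "They will be block randomized in blocks of six (except for the last block of four". It names no stratification factor. It also makes the first block of six the PK group and the group for the first safety and efficacy review.

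The imaging subset is narrower than the trial. Section 5.1 admits participants with LDL-C above 70 mg/dL, whereas Section 3.1.3 states: "We will select 12 subjects with an LDL>125 to have the imaging study". Section 8.1.1.2 repeats the threshold and gives the timing: "Subjects will have an FDG-PET/CT after screening, but prior to Day 0 and at week 28". The NIH Addendum, Section 2.1.1, makes the scan voluntary: "12 subjects will be selected to travel to the NIH CC for the optional FDG PET/CT scans". No section gives a per-arm quota, a separate list, or a rule for choosing among eligible volunteers.

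Three further assays are tied to the same people. Footnote 2 of the Schedule of Activities restricts GlycA, CEC and NMR lipoproteins: "Only for subjects completing the optional FDG-PET/CT testing". Section 8.2 says the same of each assay: "This assay will be done at the NIH for those subjects completing the optional FDG-PET/CT". By contrast, hs-CRP and endothelin-1 are collected from everyone.

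**The concern.** Permuted blocks balance consecutive enrolees. They balance a subset scattered across blocks only in part, and less so the more widely it is scattered. Exploratory objectives 1 and 3, and the GlycA part of objective 2, ask for the effect of CD24Fc, so they need usable numbers in both arms. With 12 people in total, an uneven start followed by a few missed week-28 scans could leave one arm with two or three participants, too few to estimate its mean or variance usefully. Each of the 12 will have been asked to undergo two PET/CT scans.

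**Working it through.** **The plan's own figures.** Section 9.2 uses a 15-point difference, SD 20, 80% power and two-sided 0.05. Then n = 2 × (1.960 + 0.842)² × (20/15)² = 27.9, so 28 per arm, as stated. Allowing for 11% attrition, 56/0.89 = 62.9, consistent with 64 enrolled. Section 6.3's blocks give 10 × 6 + 4 = 64, or 32:32. The documents give no sample size, power or arm split for the imaging subset.

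**Arm split if the 12 are scattered at random over the 64.** The number on CD24Fc is hypergeometric: P(k) = C(32,k) × C(32,12−k) / C(64,12). The SE of the arm difference relative to 6:6 is √[(1/k + 1/(12−k)) / (1/3)]. The detectable difference is for 80% power, two-sided 0.05, noncentral t with 10 df. The last column takes each scanned participant as completing independently with probability 0.89, which is an assumption; Section 9.2 gives 11% only for the trial as a whole.

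| Split (either way) | Probability | SE vs 6:6 | Detectable difference | P(an arm keeps ≤3 completers) |
|---|---|---|---|---|
| 6:6 | 25.0% | 1.00 | 1.80 SD | 4.1% |
| 5:7 | 41.3% | 1.01 | 1.82 SD | 10.0% |
| 4:8 | 23.0% | 1.06 | 1.90 SD | 37.3% |
| 3:9 | 8.5% | 1.15 | 2.07 SD | 100% |
| 2:10 or worse | 2.2% | 1.34 (at 2:10) | 2.41 SD (at 2:10) | 100% |

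So P(4:8 or worse) = 33.7% and P(3:9 or worse) = 10.7%. Simulating the actual block sequence gives the same values.

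**Average cost.** Weighting the SE column by the probabilities gives about 1.04. Power at a true 1.8 SD effect is 0.802, 0.791, 0.755, 0.683 and 0.555 down the rows, and its weighted average is 0.77, against 0.80 at 6:6.

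**Tail after attrition.**
- From 6:6: P(Bin(6, 0.89) ≤ 3) = 0.0206, so 1 − (1 − 0.0206)² = 4.1%.
- As written: 0.250 × 0.041 + 0.413 × 0.100 + 0.230 × 0.373 + 0.107 × 1 = 24%.
- For two or fewer completers in an arm, the same method gives 6.7% as written and 0.4% from 6:6.

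**If the 12 are the first eligible enrolees.** Block balance then partly carries over. The documents do not give the prevalence of LDL>125, so a range was simulated.

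| Assumed prevalence | P(6:6) | P(4:8 or worse) | P(3:9 or worse) |
|---|---|---|---|
| 25% | 25.9% | 31.8% | 9.4% |
| 40% | 28.9% | 26.8% | 6.4% |
| 60% | 34.1% | 18.5% | 2.8% |
| 80% | 45.6% | 8.9% | 0.5% |

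Putting the end rows through the attrition weights:
- 25%: 0.259 × 0.041 + 0.423 × 0.100 + 0.224 × 0.373 + 0.094 = 23%.
- 80%: 0.456 × 0.041 + 0.455 × 0.100 + 0.084 × 0.373 + 0.005 = 10%.

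**Side effect of a second list.** Let j of the first six enrolees be imaging participants, binomial with probability p, each list starting with its own 3:3 block. The first six overall are then 3:3 with probability about 62% at p = 12/64 and 47% at p = 0.40. Under the present single list this is certain.

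**The case against.** The strongest reply is that the loss is minor. Two splits in three are 5:7 or better, and 5:7 costs 1.4% in SE. What limits these endpoints is n = 12: even at 6:6 only differences of about 1.8 SD are detectable with 80% power, and stratifying does not change that. Leaving a small optional substudy unstratified is ordinary discretion. All of this stands, and it is why the point is a low-priority improvement.

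The 34% is also the upper end of a range. A reader might infer that the blocks do nothing for this subset, but if the first eligible volunteers are taken, some block balance carries over. The plan states no such rule, however, so it does not secure the lower risk.

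A reader might also infer that the imaging comparison is biased. The documents do not support that: the baseline scan precedes Day 0, the trial is double-blind, and unequal numbers arising by chance do not invalidate the ANCOVA of Section 9.4.2 or the unpaired t test of Section 8.2.

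Finally, Section 3.1.6 words these endpoints as changes before and after treatment, and Section 8.2 does not say which groups its t test compares. The ambiguity is real and should be cleared up. Still, Section 9.4.2 puts treatment in the model as the fixed effect and the NIH Addendum expects scans after study drug or placebo, so a between-arm reading is reasonable.

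**Conclusion.** The point holds as a modest design weakness. The arm split of the 12 imaging participants is left largely to chance, with 4:8 or worse at 34% under random scatter and about 32% to 9% under first-eligible selection. The average penalty is about 4% in SE and about 3 points of power at 1.8 SD. The case for change rests on the tail: one arm left with three or fewer scanned completers in about 24% of trials (23% to 10% under first-eligible selection), against about 4% from a 6:6 start. These figures assume exactly 12 are scanned, that attrition is 11% and independent between participants, and that LDL>125 prevalence lies between 25% and 80%. The primary LDL analysis is unaffected.

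**What to change.** Stratify the randomisation by imaging participation, confirmed by the completed baseline scan before the randomisation number is assigned. LDL>125 alone would not serve as the stratum, because the scan is optional.

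- **Imaging list:** blocks of six, two blocks for 12 participants.
- **Non-imaging list:** continue in blocks of six, with the last block sized to reach 64. With 12 imaged, 52 = 8 × 6 + 4, so the present block sizes are kept.
- **PK and first-six review group:** in Section 6.3, and wherever the text refers to the first six subjects randomised, define this group as the first complete block of one named list, for example the non-imaging list, so that it stays 3:3.
- **Contrast:** state in Section 8.2 or the SAP that the imaging-subset comparison is between arms, if that is the intention.

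The cost is a second list and a check that the scan is done before the number is assigned; there are no extra participants or procedures. There are three downsides. If fewer than 12 are scanned, each list may end in an incomplete block. The PK group is no longer strictly the first six randomised. And 6:6 holds at randomisation only if 12 are scanned; it is not protected against replacement of undosed participants under Section 7.2 or against week-28 losses.

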6.4 STUDY INTERVENTION COMPLIANCE

Since the study drug will be administered intravenously by the clinical staff in an outpatient setting. Compliance with drug administration and adherence to the protocol will be documented by clinical staff in the study record.

6.5 CONCOMITANT THERAPY

For this protocol, a prescription medication is defined as a medication that can be prescribed only by a properly authorized/licensed clinician. Medications to be reported are concomitant prescription medications, over-the-counter medications and supplements.

Information about use of concomitant medications will be collected at the screening visit and subsequent visits as outlined in section 1.3. Use of these concomitant medications (which may affect study endpoints) that exclude a participant from enrolling in the study include those outlined in Section 4.2. Additionally, medications for disease conditions excluded from the protocol (e.g., active cancer, transplantation) are not allowed in the study. Should subjects have a need to initiate treatment with any disallowed concomitant medication, the medical monitor must be consulted prior to initiation of the new medication.

6.5.1 RESCUE MEDICINE

Not applicable

7 STUDY INTERVENTION DISCONTINUATION AND PARTICIPANT DISCONTINUATION/WITHDRAWAL

7.1 DISCONTINUATION OF STUDY INTERVENTION

If a clinically significant finding is identified (including, but not limited to changes from baseline) after enrollment, the investigator or qualified designee will determine if any change in participant management is needed. Any new clinically relevant finding will be reported as an adverse event (AE).

AEs are evaluated according to the Division of AIDS (DAIDS) Table for Grading the Severity of Adult and Pediatric Adverse Events, version 2.1, July 2017. All adverse events will be reviewed by the Principal Investigator (PI) and the study team at team meetings. All Grade 3 events will be evaluated by the PI and the designated Medical Monitor. Grade 4 and Grade 5 events will be reported to the Sponsor and the Medical Monitor within 24 hours of notification of the event.

CD24Fc infusion will be paused for a single subject for any grade 4 event pending review by the Medical Monitor. The MM will include review of this event in a report issued to the DSMB every 12 weeks. Administration of medication will be paused for all subjects if 2 or more subjects have the same grade 4 adverse event deemed related to study drug. The MM will report these events to the DSMB and enrollment and dosing will be held for all pending review by the DSMB.

The study may be terminated after consultation with the Medical Monitor, DSMB and Sponsor, in the event that one or more of the following adverse reactions are not remediated within 2-4 hours, and in the opinion of the PI and Medical Monitor, are clinically relevant and constitute a substantial risk to the participants: cytokine release syndrome, hypotension, shortness of breath, disseminated intravascular coagulation, mental status changes.

Other criteria for study termination may include:

- the decision of the Medical Monitor or DSMB to stop further study visits
- the recommendation or decision for any reason of the PI that safety may be at risk or compromised by continuing the trial
- the decision of the Sponsor to terminate the study for any reason

The data to be collected at the time of study intervention discontinuation will include the following:

- Vital signs and physical examination
- Complete metabolic panel, complete blood count with differential, PT/INR
- Other laboratory tests that further evaluate a sign or symptom
- Procedures for further evaluation of lab abnormalities or symptoms

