7.2 PARTICIPANT DISCONTINUATION/WITHDRAWAL FROM THE STUDY

Participants are free to withdraw from participation in the study at any time upon request.

An investigator will discontinue or withdraw a participant from the study for the following reasons:

- Pregnancy or breastfeeding
- Significant study intervention non-compliance
- Any clinical adverse event (AE), laboratory abnormality, or other medical condition or situation which occurs such that continued participation in the study would not be in the best interest of the participant (including malignancy)
- New or recurrent Centers for Disease Control and Prevention (CDC) category C AIDS-indicator condition.
- If the participant meets an exclusion criterion (either newly developed or not previously recognized) that precludes further study participation
- Participant unable to receive CD24Fc for 2 doses

- Development of life-threatening infection or clinical reason deemed to be life-threatening by the physician
- Request of the primary care provider or Investigator if s/he thinks the study is no longer in the best interest of the subject.
- If the subject is judged by the Investigator to be at significant risk
- The following laboratory abnormalities
 - HIV RNA>200 copies/mL (2 readings at least 2 weeks apart)
 - o Decrease in eGFR to <30mL/min, confirmed by immediate repeat testing
 - Elevation of ALT >5x OR AST >5x Day 0, confirmed by immediate repeat testing
 - Abnormal elevation of ALT >3 x Day 0 and total bilirubin >2 x ULN, confirmed by immediate repeat testing
 - For participants with entry CD4+ T cell count between 350 500 cells/mm³, confirmed absolute and percent CD4+ decline greater than 25% of baseline.
 - For participants with entry CD4+ T cell count between 501 to 800 cells/ mm³, a confirmed absolute and percent CD4+ T cell decline greater than 33% of baseline.
 - For participants with entry CD4+ T cell count greater than 800 cells/ mm³, a confirmed absolute and percent CD4+ T cell decline greater than 50% of baseline.
 - Occurrence of Grade 4 anemia/neutropenia or recurrence of Grade 3 anemia/neutropenia.

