8.4.3 CLASSIFICATION OF AN ADVERSE EVENT

8.4.3.1 SEVERITY OF EVENT

The investigator will grade the severity of each AE according to the "Division of AIDS Table For Grading The Severity Of Adult and Pediatric Adverse Events", version 2.1, July 2017. https://rsc.niaid.nih.gov/sites/default/files/daidsgradingcorrectedv21.pdf

For adverse events (AEs) not included in the protocol defined grading system, the following guidelines will be used to describe severity.

- **Grade 1-Mild** Causing no or minimal interference with usual social and functional activities with intervention not indicated.
- **Grade 2-Moderate** Causing greater than minimal interference with usual social and functional activities with intervention indicated.
- **Grade 3-Severe** Causing inability to perform usual social and functional activities with intervention or hospitalization indicated.
- **Grade 4-Potentially Life Threatening** Causing inability to perform basic self-care functions with intervention indicated to prevent permanent impairment, persistent disability or death.
- Grade 5-Death

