3 CRITERIA FOR REMOVAL FROM SPONSOR PROTOCOL

Per sponsor protocol section **6.2 Participant Discontinuation/Withdrawal from the Study**, study participation could be discontinued due to the following reasons:

- Pregnancy or breastfeeding
- Significant study intervention non-compliance
- Any clinical adverse event (AE), laboratory abnormality, or other medical condition or situation which occurs such that continued participation in the study would not be in the best interest of the participant (including malignancy)
- New or recurrent Centers for Disease Control and Prevention (CDC) category C AIDS-indicator condition.
- If the participant meets an exclusion criterion (either newly developed or not previously recognized) that precludes further study participation
- Participant unable to receive CD24Fc for 2 doses
- Development of life-threatening infection or clinical reason deemed to be life-threatening by the physician
- Request of the primary care provider or Investigator if s/he thinks the study is no longer in the best interest of the subject.
- If the subject is judged by the Investigator to be at significant risk
- The following laboratory abnormalities
 - HIV RNA>200 copies/mL (2 readings at least 2 weeks apart)
 - Decrease in eGFR to <30mL/min, confirmed by immediate repeat testing

NIH ADDENDUM TO THE MAIN/SPONSOR PROTOCOL (this needs to be read in conjunction with the main/sponsor protocol) Abbreviated Title: CALIBER

Version Date: 01/13/2020

- Elevation of ALT >5x OR AST >5x Day 0, confirmed by immediate repeat testing
- Abnormal elevation of ALT >3 x Day 0 and total bilirubin >2 x ULN, confirmed by immediate repeat testing
- For participants with entry CD4+ T cell count between 350 500 cells/mm³, confirmed CD4+ decline greater than 25% of baseline.
- For participants with entry CD4+ T cell count between 501 to 800 cells/ mm³, a confirmed CD4+ T cell decline greater than 33% of baseline.
- For participants with entry CD4+ T cell count greater than 800 cells/ mm³, a confirmed CD4+ T cell decline greater than 50% of baseline.
- Occurrence of Grade 4 anemia/neutropenia or recurrence of Grade 3 anemia/neutropenia.

4 SAFETY REPORTING REQUIREMENTS/DATA AND SAFETY MONITORING PLAN (THIS REPORTING SECTION OUTLINES THE REPORTING REQUIREMENTS THAT ARE REQUIRED TO THE NIH AND ARE IN ADDITION TO THE REPORTING REQUIREMENTS FOR THE UMB IRB.)

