Enrollment and dosing will be paused for an individual subject who has a Grade 4 AE. After review by the Medical Monitor (MM) and reporting to the DSMB in the regularly scheduled report every 12 weeks, the MM will evaluate whether study participation for the subject should continue. During MM review, enrollment and dosing will not be paused for other study subjects.

If two subjects experience the same Grade 4 AE related to the study drug, all enrollment will be paused and all doses for enrolled subjects will be held. The MM will report to the DSMB within 24 hours and study dosing will halt until DSMB determination regarding continuation of study enrollment and dosing.

If one or more subjects experiences changes in mental status, DIC, dyspnea, cytokine release syndrome and/or hypotension related to the study drug, without remediation in 2-4 hours, the MM will report to the DSMB within 24 hours and the DSMB will review the report for possible study termination. During this review, enrollment and dosing will be halted for all subjects.

Safety and Efficacy Analyses

The primary safety endpoint will be assessed by Incidence and severity of any adverse events (AEs) during the administration of drug and 24 weeks after completion. Safety will be evaluated by assessment of clinical laboratory tests, physical examination at various time points during the study, and by the documentation for AEs. A statistical analysis plan (SAP) will be prepared and finalized prior to unblinding of subject's treatment assignment. This document will provide further details regarding the definition of analysis variables and analysis methodology to address all study objectives.

Safety and tolerability will be summarized by treatment arm, including Treatment Emergent Adverse events (TEAEs), and laboratory evaluations. No inferential analysis is planned for safety data. Adverse events will be coded using the most current version of the Medical Dictionary for Regulatory Activities

(MedDRA). TEAEs are defined as new or worsening AEs after the first dose of study medication, and will be summarized by system organ class, and preferred term. A list of subjects who have Severe Adverse Events (SAEs) and who discontinue from the study due to an adverse event will be provided.

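### For Grade 4 anemia or neutropenia, and for a Grade 4 event a physician deems life-threatening, the pause-and-review rule (7.1, Appendix A) and the withdrawal list (7.2) give different outcomes and decision-makers, with no precedence stated

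*Combined protocol and SAP*

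**What the plan says.** Four places in the combined protocol deal with what happens to one participant after a severe event.

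- **Section 7.1 (Discontinuation of Study Intervention):** "CD24Fc infusion will be paused for a single subject for any grade 4 event pending review by the Medical Monitor". No time limit is set for the review.
- **Appendix A (Pausing and Halting Rules):** "Enrollment and dosing will be paused for an individual subject who has a Grade 4 AE". After review and reporting to the DSMB, "the MM will evaluate whether study participation for the subject should continue".
- **Section 7.2 (Participant Discontinuation/Withdrawal):** "An investigator will discontinue or withdraw a participant from the study for the following reasons". The list includes "Occurrence of Grade 4 anemia/neutropenia or recurrence of Grade 3 anemia/neutropenia" and "Development of life-threatening infection or clinical reason deemed to be life-threatening by the physician".
- **NIH Addendum, section 3:** the same list, introduced by "study participation could be discontinued due to the following reasons".

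Section 8.4.9, which should hold the pausing and halting rules, only refers the reader to Appendix A. Section 7.2 adds that treated participants who are later withdrawn are not replaced. It also says that those who stop the agent because of toxicity remain on the assessment schedule if willing.

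**The concern.** A participant with Grade 4 neutropenia after the first infusion meets the condition in 7.1, the condition in Appendix A and the condition in 7.2. Under the first two, dosing is paused and continuation stays open, with the Medical Monitor deciding in Appendix A. Under 7.2 the investigator is to discontinue or withdraw the participant, and no review is mentioned. Site staff following different sections could handle two identical cases differently. One participant might go on to further infusions and the other might leave the study. These are safety rules in a double-blind trial, so such cases should be handled by a stated rule and not by whichever section was read.

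**Working it through.** The trial's sample size and power do not enter here. The check sets the rules side by side and adds simple date arithmetic.

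**Step 1. Which events meet both rules?**

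| Event | 7.1 and Appendix A | 7.2 |
|---|---|---|
| Grade 4 anemia or neutropenia | Pause; Medical Monitor review | Discontinue or withdraw (named by grade) |
| Grade 4 event a physician deems life-threatening | Pause; Medical Monitor review | Discontinue or withdraw (by judgment) |
| Other Grade 4 event | Pause; Medical Monitor review | Not listed by grade; applies only if another listed reason is met |

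The first row is a direct overlap. The second depends on a physician's finding. The third is not in conflict on its face.

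**Step 2. Does any text settle the order?** The single-participant pause in 7.1 and in Appendix A covers Grade 4 events without exception, and neither text mentions the 7.2 reasons. Section 7.2 does not mention the pause. Section 8.4.9 leads only to Appendix A.

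**Step 3. Is the 7.2 list mandatory?** The protocol says *will*; the Addendum says *could*. The Addendum carries a January 2020 date and protocol version 5.0 a November 2020 date, so its wording may simply not have been updated. It is nevertheless bound into the current document, with an instruction to read it together with the main protocol.

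**Step 4. How much treatment depends on it?** Three infusions are planned, at Day 0, Week 2 and Week 4.

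- Event after the first infusion and before the second: 3 − 1 = 2 infusions at stake.
- Event after the second and before the third: 3 − 2 = 1 infusion at stake.
- Event after the third: 3 − 3 = 0 infusions, but study status (withdrawn or followed) is still at stake.

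**Step 5. Could dosing resume after a pause?** Section 8.1 allows ±4 days, so the last in-window dose is at about Day 28 + 4 = Day 32. From an event on Day 1, 15 or 28 (the last before the third infusion), 32 − 1 = 31, 32 − 15 = 17 or 32 − 28 = 4 days remain. Appendix A places the Medical Monitor's evaluation after reporting in a 12-weekly report, and 12 × 7 = 84 days. If the decision had to wait a full cycle, no dose could resume. After an event between the first two infusions, two doses would then be missed, which is itself a 7.2 reason. Under 7.1 the pause waits only for the Medical Monitor's review, so resumption within the window is possible. The outcome therefore depends on which text is followed.

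**The case against.** The strongest reply is that the rules work in sequence: pause at once, then withdraw if a 7.2 reason is met. Nothing in 7.1 or Appendix A says dosing must resume, and the Medical Monitor's evaluation could end in withdrawal. This reading is possible, and it is why the point is an unresolved overlap rather than a flat contradiction. But the text does not state it. If 7.2 applied automatically, the Medical Monitor would have no continuation question left for these events, yet Appendix A assigns that question for every Grade 4 event.

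A second reply is that 7.1 concerns the drug and 7.2 the study. That helps for 7.1. It does not help for Appendix A, where the Medical Monitor's question is about study participation, the same subject as 7.2.

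A third is that the investigator acts throughout, since 7.1 opens by giving the investigator decisions on participant management. That is fair and softens the contrast, but for Grade 4 events Appendix A still gives the evaluation to the Medical Monitor.

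Several stronger readings are tempting, and the documents do not support them.

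- A reader might infer that every Grade 4 event requires withdrawal, from the label "Grade 4-Potentially Life Threatening" in 8.4.3.1. That scale applies only to events outside the DAIDS grading table, and a grade label is not a physician's finding that an event is life-threatening.
- A reader might infer that primary endpoint 1 is distorted. It counts the incidence and severity of adverse events, and the triggering event counts the same whether the participant is paused or withdrawn.
- A reader might infer that each case costs a Week 6 LDL value and set an assumed rate against the planned losses. For instance, 2–10% of 64 gives 64 × 0.02 = 1.3 to 64 × 0.10 = 6.4 participants, against 64 − 56 = 8. That rate would cover all Grade 4 events, most of which may not meet both rules, and it is not limited to the dosing period. Section 7.2 also keeps those who stop only the agent on the assessment schedule, and the mITT set keeps anyone dosed at least once.

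**Conclusion.** The concern holds in a narrow form. For Grade 4 anemia or neutropenia, and for a Grade 4 event that a physician deems life-threatening, the documents state two rules with different outcomes and different decision-makers, and do not say which prevails. The Addendum adds doubt about whether the 7.2 list is binding.

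The consequence for a given participant is whether up to two remaining infusions may be given, and whether the participant is withdrawn or followed on schedule. Withdrawal could mean a missing Week 6 LDL, but that does not follow in every case. No rate for these events in this population is given, so no count of affected participants is claimed. The conclusion rests on the wording alone and takes no position on which rule is clinically right.

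**What to change.** Reconcile section 7.1, section 7.2, Appendix A and section 3 of the NIH Addendum so that each of these events leads to one action and one decision-maker.

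- State in 7.1 and in Appendix A how the pause-and-review rule relates to events that 7.2 also lists.
- Make clear in 7.2 whether each of these events ends study drug only or study participation as well.
- Use the same force of wording, mandatory or permissive, in 7.2 and the Addendum.

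Which action applies is for the sponsor and its safety board to decide. The cost is amendment wording in four places; no new procedure, visit or analysis is needed.
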